8.2 ADVERSE EVENTS (AEs)

An adverse event is any untoward medical occurrence, unintended disease or injury, or untoward clinical signs (including abnormal laboratory findings) in subjects, users or other persons, whether or not related to the investigational medical device.

Note 1 to entry: This definition includes events related to the investigational medical device or the comparator.

Note 2 to entry: This definition includes events related to the procedures involved.

Note 3 to entry: For users or other persons, this definition is restricted to events related to the use of investigational medical devices.

8.3 SERIOUS ADVERSE EVENT (SAE)

An adverse event that led to any of the following:

- a) death,
- b) serious deterioration in the health of the subject, users or other persons as defined by one or more of the following:
 - 1) a life-threatening illness or injury, or
 - 2) a permanent impairment of a body structure or a body function including chronic diseases, or
 - 3) in-patient or prolonged hospitalisation, or
 - 4) medical or surgical intervention to prevent life-threatening illness or injury or permanent impairment to a body structure or a body function,
- c) foetal distress, foetal death or a congenital abnormality or birth defect including physical or mental impairment

Note 1 to entry: Planned hospitalisation for a pre-existing condition, or a procedure required by the CI without serious deterioration in health, is not considered a serious adverse event.

8.4 SERIOUS ADVERSE DEVICE EVENT (SADE)

A serious adverse device effect (SADE) is any adverse device effect that has resulted in any of the consequences characteristic of a serious adverse event. A SADE may be anticipated or unanticipated.

Anticipated serious adverse device effect (ASADE) is an effect which by its nature, incidence, severity or outcome has been identified in the risk analysis report.

Unanticipated serious adverse device effect (USADE) is a serious adverse device effect which by its nature, incidence, severity or outcome has not been identified in the current version of the risk analysis report.

8.5 RECORDING AND REPORTING OF ADVERSE EVENTS

Reports of non-serious Adverse Events (AE), Serious Adverse Events (SAE), serious adverse device events (SADE) or other errors outside of what is foreseen in the protocol (irrespective if a clinical event has occurred) will be reported to the CI and will be submitted to the Research Ethics Committee (REC) using the Non-CTIMP safety report to REC form.

Only reports of SAEs, non-serious AEs or SADEs that are 1. related to the study (i.e. they resulted from administration of any of the research procedures) and 2. unexpected (USADE) should be submitted.

These should be sent within 15 days of the CI becoming aware of the event. There is no requirement for annual safety reports in addition to the information provided through the annual progress report.

9 STATISTICS AND DATA ANALYSIS

9.1 STATISTICAL ANALYSIS PLAN

The study will have a comprehensive Statistical Analysis Plan, which will govern all statistical aspects of the study, and will be agreed by the Trial Management Group (TMG) before any unblinded data is seen.

The primary outcomes measures are changes in functional connectivity and neuronal signal cohesion as measured by 7T MRI and changes in glutamate signal in the L-IPL as measured by 7T MRS, before and after TMS/sham procedure in patients with RA.

The secondary outcome measures are changes in pain severity, changes in RA disease activity, changes in putative pain confounders and changes in inflammatory cytokines/chemokines before and after TMS/sham procedure in patients with RA.

1) Descriptive statistics and data visualization. Median values and interquartile ranges of primary and secondary outcomes will be generated for each of the four time points. Paired plots for raw data and boxplots will be generated showing difference scores in the outcomes following sham and active TMS.

2) Hypothesis testing. Paired-difference tests for parametric data (paired sample t-tests) will be used to test our hypotheses by comparing the change in outcomes following sham TMS to the change in outcomes following active TMS. Hypothesis testing will be two-sided with alpha = .05, and 95% confidence intervals around the contrast will be generated using bootstrapping with 20,000 resamples.

3) Effect Size: As a simple expression of effect size, the proportion of subjects showing greater, equal and lesser reduction in glutamate between active and sham conditions will be reported. For the calculation of sample size estimates for future studies, the standardized mean difference effect size for within-subject designs (d-z) will be calculated (Reference 40).

4) Outcome inter-relationships: Exploratory correlations will examine the relationships between the different outcomes and their change

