Rationale	Many patients with rheumatoid joint disease continue to experience significant pain despite receiving apparently optimal joint specific therapies. We believe this discrepancy relates to the existence of pain sources which are supplementary to those present in the joints. In particular, we have been among the first to report evidence implicating the brain in the generation of this disabling problem. Brain scanning methods have helped us to identify a specific region (the left inferior parietal lobule (L-IPL)) which appears to be an important link between the characteristic excessive inflammation of RA and pain processing. We hope to better examine this possible link by employing a safe, non-invasive technique called transcranial magnetic stimulation (TMS). TMS uses a magnet to influence the function of a specific region on the brain surface. We will use TMS to target the left inferior parietal lobule and then assess participants for changes in aspects of brain biology (which have been considered important in other chronic pain disorders), their pain and markers of inflammation. Due to the inherent dangers of sampling the brain, we will instead use 7T magnetic resonance imaging to make indirect measurements of brain biology, including changes in specific chemistry. This information will help us to better understand the precise role of the left inferior parietal lobule in relation to pain. The results of this modest project will inform bigger, more definitive studies and will ultimately deliver knowledge that will allow us to address the tremendous shortfall of safe and effective pain relief strategies for patients with RA and beyond.
Methodology	This randomised, sham-controlled, crossover study will allow us to test the hypothesis that systemic inflammation results in haphazard neuronal signalling and heightened centralised pain using a single session of non-invasive TMS. In order to ensure that any observed changes are specific to TMS, subjects will be randomised equally to receive an initial single session of either active or sham procedure. The latter will employ the same equipment but will not generate a magnetic effect. Subjects will be asked to return 3 weeks later to receive the alternative procedure.
Sample Size	20 participants

Screening	Patients with active RA attending clinics in NHS Greater Glasgow and Clyde will be approached to contribute to this study by the point of care team.

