Statistical Analysis	
1) Descriptive statistics and data visualization. Median values and interquartile ranges of primary and secondary outcomes will be generated for each of the four time points. Paired plots for raw data and boxplots will be generated showing difference scores in the outcomes following sham and active TMS.
 
2) Hypothesis testing. Paired-difference tests for parametric data (paired sample t-tests) will be used to test our hypotheses by comparing the change in outcomes following sham TMS to the change in outcomes following active TMS. Hypothesis testing will be two-sided with alpha = .05, and 95% confidence intervals around the contrast will be generated using bootstrapping with 20,000 resamples.
 
3) Effect Size: As a simple expression of effect size, the proportion of subjects showing greater, equal and lesser reduction in glutamate between active and sham conditions will be reported. For the calculation of sample size estimates for future studies, the standardized mean difference effect size for within-subject designs (d-z) will be calculated.
 
4) Outcome inter-relationships: Exploratory correlations will examine the relationships between the different outcomes and their change

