5.6 RANDOMISATION & BLINDING

This is a randomised, sham-controlled, crossover study. Once participants have given consent and been fully screened for study eligibility, they will be randomised to receive either a single session of active TMS procedure to the L-IPL or a TMS sham procedure which will not modulate the brain. Provided the first session causes no reason to withdraw the participant, they will return 3 weeks later to receive the alternative TMS procedure to that they had undergone originally.

In order to optimise participant blinding, we will employ a sham coil which mimics the clicking and scalp sensations.

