6.1.3 Visit 1 (Day 14) (+/- 7 days)

Visit 1 will be conducted at the Queen Elizabeth University Hospital

- 7T Neuroimaging protocol*
- Michigan Body Map Regional Pain[§]
- NRS for pain, fatigue, and depression*
- McGill Pain Questionnaire[§]
- Disease activity (SDAI / CDAI)
- Sickness Questionnaire*
- Pain confounder questionnaires[§]:
 - PROMIS-Fatigue (16-items)[§]
 - PROMIS-Depression (8 items)[§]
 - PROMIS-Anxiety (8 items)[§]
 - PROMIS-Sleep Related Impairment (8 items)[§]
 - PROMIS-Physical Functioning Short Form (8-items)[§]
 - PROMIS-Pain Interference (8-item)[§]

- ACR Fibromyalgia Scale[§]
- Venous blood sample for peripheral immunophenotyping*
- TMS or sham procedure
- Completion of symptom diary (to be done at home, Days 15-21)

**will be conducted before and after TMS/sham procedure*

§has the option to be completed remotely to reduce visit time

Estimated visit time 4 hours

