6.3 STUDY OUTCOME MEASURES

6.3.1 Primary Outcome Measure(s)

The primary outcome measures will be:

1. Changes in functional connectivity and neuronal signal cohesion as measured by 7T MRI
2. Changes in glutamate signal in the L-IPL as measured by 7T MRS

before and after TMS/sham procedure.

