6.3.2 Secondary Outcome Measure(s)

The secondary outcome measures will be:

1. Changes in pain severity as measured by the Pain NRS
2. Changes from the Michigan Body Map Regional Pain
3. Changes in RA disease activity as measured by SDAI, CDAI
4. Changes in putative pain confounders as measured by PROMIS-Fatigue, PROMIS-Depression, PROMIS-Anxiety, PROMIS-Sleep Related Impairment, PROMIS-Physical functioning short form, PROMIS-Pain Interference and ACR Fibromyalgia Scale
5. Changes in blood protein levels of inflammatory cytokines/chemokines

before and after TMS/sham procedure (1) and (5).

before TMS/sham procedure (2), (3) and (4).

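### The order of active and sham TMS is randomised, but the fixed paired t-test ignores period; adding a period adjustment costs one degree of freedom

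*Protocol*

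**What the plan says.** Protocol section 5.6 states the design: "This is a randomised, sham-controlled, crossover study". The synopsis (Methodology) adds that "subjects will be randomised equally to receive an initial single session of either active or sham procedure", with the other procedure three weeks later, in 20 participants.

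Section 9.1 item 2 and the synopsis (Statistical Analysis) name the test: "Paired-difference tests for parametric data (paired sample t-tests) will be used to test our hypotheses". The contrast is the within-participant difference between the two change scores, active against sham. The test is two-sided at 0.05, with a bootstrap 95% confidence interval from 20,000 resamples. Neither place mentions period, sequence or resampling within sequence.

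Section 9.1 item 3 gives the result a further use: "For the calculation of sample size estimates for future studies, the standardized mean difference effect size for within-subject designs (d-z) will be calculated".

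On timing, section 6.3.1 takes the primary imaging outcomes "before and after TMS/sham procedure", and the footnote to the Visit 1 list in section 6.1.3 says the asterisked items "will be conducted before and after TMS/sham procedure"; Visit 3 is the same. The body map, SDAI/CDAI and PROMIS scales carry no asterisk and are collected once per visit. Section 9.1 also says that a separate Statistical Analysis Plan will govern all statistical aspects; it is not available here.

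**The concern.** The trial randomises order, and the fixed test then discards it. A crossover contrast contains the treatment effect plus or minus any difference between periods, with the sign set by the sequence. Averaging over equal sequences removes that difference from the estimate but not from the paired t-test's SD. If the sequences end unequal, it stays in the estimate too.

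Which period effects matter depends on the outcome:

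- **Imaging, pain NRS and bloods**, when compared before and after the procedure within one visit: slow drift cancels. Only a period effect on the change itself matters, for example a first session in the scanner and under the coil behaving differently from a second.
- **Body map, SDAI/CDAI and PROMIS**, measured once per visit: on the visit schedule a change runs from Visit 1 to 2 and from Visit 3 to 4. Participants enter on raised CRP or ESR and a swollen joint, so regression to the mean or non-linear drift can differ between the two intervals.

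Unequal sequences are foreseeable. Section 5.6 makes the second session conditional on the first giving no reason to withdraw, and section 5.7 allows withdrawal at any time. At stake are the power of the contrast, the accuracy of its point estimate, and the d-z that is to size later studies.

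**Working it through.** **Inputs from the protocol.** N = 20, equal allocation to two sequences, paired t-test, two-sided alpha 0.05. Section 9.4 gives no power, effect size or SD, so there is no stated figure to reproduce.

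**Assumed inputs.** SD of the within-participant contrast (active change minus sham change) = 1. Treatment effect tau = 0.66, which gives 80% power for a paired t-test at n = 20 (noncentral t, 19 df; exact value 0.6604). Period effect pi = mean change score in period 2 minus period 1, from 0 to 1 SD.

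**Model.** The contrast has mean tau - pi when active comes first and tau + pi when sham comes first.

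**Estimators compared.**
- Paired t: mean of all contrasts, n-1 df.
- Period-adjusted: average of the two sequence means, pooled within-sequence variance, n-2 df.

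**Bias of the paired estimate** = pi x (n sham-first - n active-first)/N. As a share of pi it is 1/19 = 5% at 10/9, 2/18 = 11% at 10/8 and 4/16 = 25% at 10/6. At 10/6 with |pi| = 0.5 that is 0.25 x 0.5 = 0.125 SD. The adjusted estimate has no bias at any split.

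**Power and type I error at 10/10** (400,000 simulated trials per setting):

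| pi | Paired-t power | Adjusted power | Paired-t type I error |
|---|---|---|---|
| 0 | 80.1% | 79.9% | about 5% |
| 0.10 | 79.8% | 79.8% | not tabulated |
| 0.25 | 78.2% | 79.8% | 4.3% |
| 0.5 | 72.3% | 79.8% | 2.9% |
| 1.0 | 49.5% | 79.8% | 0.6% |

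**Unequal sequences, |pi| = 0.5.** At 10/8, paired-t power is about 58% or 74% depending on the sign of pi, against 74% adjusted. At 10/6 it is 43% or 77%, against 66% adjusted. The higher paired figure at 10/6 arises because the bias there exaggerates the effect. Paired-t type I error stays at or below 5% in both.

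**d-z.** With equal sequences the unadjusted SD is about sqrt(1 + pi^2), so d-z is about 0.66/sqrt(1 + pi^2):
- pi 0.25: 0.66/1.031 = 0.64
- pi 0.5: 0.66/1.118 = 0.59
- pi 1.0: 0.66/1.414 = 0.47

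At 80% power and two-sided 0.05, a crossover needing 20 participants would be sized at 22, 25 and 38. The first and last figures move by one (21 and 39) with the third decimal of the benchmark and a small-sample factor in the SD.

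**Cost of adjusting when pi = 0** (exact power, paired v adjusted):
- 10/10: 80.0% v 79.8%
- 10/9: 77.7% v 77.3%
- 10/8: 75.2% v 74.4%
- 10/6: 69.5% v 66.3%

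**Bootstrap interval.** In simulation at 10/10, a within-sequence percentile interval covered about 92% and a studentised one about 95%.

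**The case against.** The arithmetic is not in dispute. The case against is about likelihood and importance.

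- **The governing SAP could add period.** It could, but the protocol already names the test in two places. If the SAP adds the term, the protocol wording still has to be aligned with it.
- **The mechanism is thin for the primary outcomes.** Same-visit changes cancel drift, and the protocol offers no evidence of a first-session effect. This stands as a limit on likelihood.
- **It is weaker than it looks for the secondary outcomes.** Selection is at Day 0 and Visit 1 at Day 14, so some regression to the mean is over before period 1. Visit 1 to 2 and Visit 3 to 4 are both nominally 14 days, so linear drift cancels. Only slowly decaying or non-linear components remain. That is fair.
- **The striking figures need large pi.** A pi of 0.5 is 76% of the benchmark treatment effect (0.5/0.66). The 10/6 split needs four losses from one sequence, with probability about 9% if four losses fall at random (2 x C(10,4)/C(20,4) = 420/4845). At pi 0.25 the mean squared errors of the two estimates are practically equal: 0.0563 for both at 10/8, and 0.0664 paired against 0.0667 adjusted at 10/6. This also stands.
- **Precision.** At 10/10 the two point estimates are the same number. The loss lies in the estimated standard error, hence in power and interval width.
- **d-z.** The diluted value misleads only if the next study is a crossover analysed with period. Its shift (0.02 at pi 0.25, 0.07 at 0.5) is also small beside sampling error, with a 95% interval of about 0.17 to 1.14 around an observed 0.66 at n = 20. Both are true, but a systematic understatement that can be avoided at almost no cost is still worth avoiding.

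The bootstrap coverage problem comes from the small sample, not from omitting period. It belongs here only because the interval has to be respecified with the estimator.

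**Conclusion.** The concern holds. The protocol fixes an analysis that ignores the randomised order. Given a material period effect on the change score, that analysis gives a standard error that is too large, a d-z that is too small for sizing a period-adjusted crossover, and a biased estimate when completers differ by sequence.

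The effect is negligible at pi 0.10, modest at 0.25, about 7.5 points of power at 0.5 (79.8 - 72.3) and about 30 points at 1.0 (79.8 - 49.5). It rests on an assumed range for pi and a benchmark effect of 0.66 SD; the protocol gives neither. False positives do not rise in the settings examined, where the paired test is at or below its nominal level. This should be changed because the remedy is cheap and the trial is small, but it does not threaten the validity of the trial.

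**What to change.** - **Section 9.1 item 2 and the synopsis:** replace the paired t-test with a period-adjusted crossover analysis. Estimate the effect as the average of the two sequence means of the within-participant active-minus-sham differences, with pooled within-sequence variance on n-2 df. For complete pairs this equals a linear model with treatment, period and participant.
- **Bootstrap:** resample within sequence and use a studentised interval by default.
- **Section 9.1 item 3:** compute d-z with the within-sequence SD, and say so where it is reported for future sizing.
- **Optional:** fit participant as a random effect so that those with one session contribute. The gain is modest.

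The cost is wording in three places and one degree of freedom. If there is no period effect, that is about 0.2 points of power at 10/10 and about 3 at 10/6. No extra data or visits are needed. Section 9.1 has the SAP agreed before unblinded data are seen, so the change can be pre-specified there and in the protocol together.

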SADE	Serious Adverse Device Event
SDAI	Simple Disease Activity Index
7T	Tesla
TMG	Trial Management Group
TMS	Transcranial magnetic stimulation

STUDY SYNOPSIS

Title of Study	Probing the Rheumatoid Arthritis Brain to Elucidate Central Pain Pathways
Study Centre	University of Glasgow/NHS Greater Glasgow and Clyde
Duration of Study	24 months
Primary Objective	To evaluate changes in neural glutamate, neuronal signal cohesion and functional connectivity in RA patients following L-IPL stimulation using TMS
Secondary Objective	To evaluate changes in pain severity and characterisation, RA disease activity, sickness behaviour and peripheral inflammatory markers in RA patients following L-IPL stimulation using TMS
Primary Endpoints	The primary endpoints are - Changes in functional connectivity and neuronal signal cohesion after TMS/sham therapy, as measured by 7T MRI - Changes in glutamate signal in the L-IPL after TMS/sham therapy, as measured by 7T MRS

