As a critical first step, this feasibility study aims to pilot a transcranial magnetic stimulation (TMS) protocol designed to target the L-IPL in RA. We will evaluate its effect employing ultra-high resolution 7T functional and glutamate measures. This novel project will inform a larger study which will aim to provide more robust evidence for the proposed neural pain interface between systemic inflammation and pain. Such knowledge could potentially support the analgesic testing of existing compounds e.g. alternative/augmented immunosuppressants or neural glutamate modulatory agents; and reverse translated in order to more precisely dissect the culprit mechanisms which in turn may inform the development of novel pain therapeutics. Both represent core aims of Versus Arthritis and address critical priorities among the patient populations that we serve.

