3.3 STUDY HYPOTHESIS

We believe that the left inferior parietal lobule of the brain is a key region where inflammation and pain communicate in RA. Specifically, we hypothesise that inflammation leads to high levels of glutamate in the left inferior parietal lobule and subsequent haphazard functioning of this area. This then leads to abnormal communication with other regions of the brain such as those known to be important to pain processing in fibromyalgia. Ultimately, we expect these processes to alter patients' overall experience of pain.

If correct, we would expect a normalisation of left inferior parietal lobule activity to reduce glutamate levels and rebalance the functioning of the proposed pain systems in 'inflamed' RA patients.

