5 STUDY DESIGN

The study design is detailed below and is summarised in the STUDY FLOW CHART and **Error! Reference source not found.** The trial is a single-centre, randomised sham-controlled crossover study to test the hypothesis that normalisation of left inferior parietal lobule activity using TMS will reduce glutamate levels and rebalance the functioning of the proposed pain systems in 'inflamed' RA patients.

All of the study research data/ indices including the outcomes of study measures and samples will be shared with our collaborators in the University of Michigan. No personal data will be exported to our co-investigators at University of Michigan, but non-personal information may be transferred. The data transferred to the University of Michigan will include the study code/age/gender and questionnaire data. The University of Michigan will not have access to the pseudoanonymised key which will be kept within NHS GG&C only, therefore data will be anonymised to the University of Michigan investigators and pseudoanonymised to NHS GG&C/University of Glasgow investigators. The University of Michigan will undertake collaborative analyses; an appropriate Data Transfer Form and Controller to Controller Agreement will be completed.

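### Does the protocol contradict itself on what a primary p-value below 0.05 would mean, by stating one joint hypothesis and testing several primaries?

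*Protocol*

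**What the plan says.** Four parts of the protocol bear on this.

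- **Tests.** Section 9.1, item 2: paired t-tests "will be used to test our hypotheses by comparing the change in outcomes following sham TMS" with the change following active TMS. "Hypothesis testing will be two-sided with alpha = .05", with bootstrap 95% confidence intervals. Item 3 adds the within-subject effect size d-z for planning later studies. In item 4, "Exploratory correlations will examine the relationships between the different outcomes and their change". Section 9.1 also hands the statistical aspects to a separate SAP, which the Trial Management Group is to agree before unblinded data are seen.
- **Hypothesis.** Section 5 presents the trial as a "study to test the hypothesis that normalisation of left inferior parietal lobule activity using TMS will reduce glutamate levels and rebalance the functioning"; the functioning meant is that of the pain systems. Section 3.3 gives the same expectation: "normalisation of left inferior parietal lobule activity to reduce glutamate levels and rebalance the functioning of the proposed pain systems". The Methodology row of the synopsis says the study "will allow us to test the hypothesis that systemic inflammation results in haphazard neuronal signalling and heightened centralised pain".
- **Status.** Section 3.2: "this feasibility study aims to pilot a transcranial magnetic stimulation (TMS) protocol designed to target the L-IPL in RA". It adds that a larger study will follow to give firmer evidence.
- **Primaries.** The primary objective in the synopsis is "To evaluate changes in neural glutamate, neuronal signal cohesion and functional connectivity in RA patients" after stimulation. Sections 4.1 and 6.3.1 list two items, one for MRI (connectivity and signal cohesion) and one for MRS (glutamate). No ranking is given.

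**The concern.** Three features look like disagreements about what the primary tests are for.

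1. The hypothesis in sections 3.3 and 5 has two parts joined by a conjunction, while section 9.1 speaks of several hypotheses and applies one alpha to univariate tests.
2. The synopsis states a hypothesis about inflammation, section 5 one about TMS, and section 3.2 a feasibility aim. In 9.1 only the correlations are called exploratory, so the primary tests could be taken as confirmatory.
3. The primary objective names three constructs but the endpoint lists have two entries.

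If these were real contradictions, a mixed result, with some primaries significant and others not, could be reported either as support for the hypothesis or as lack of it, and the choice could be made after seeing the data. With 20 participants a mixed result is plausible, and the findings are meant to shape a larger study.

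**Working it through.** There is no figure in the plan to reproduce: section 9.4 gives no power, effect size or standard deviation. The check is first of the text, then of the size of what would be at stake.

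**Text, point by point**

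1. *One hypothesis or several.* Section 4 lists the objectives separately: connectivity and cohesion; glutamate in the L-IPL; pain severity and disease activity. Plural hypotheses tested outcome by outcome in 9.1 correspond to that list. Section 5 is a mechanistic statement. It does not say that every component must reach significance, so there is no all-must-succeed rule for 9.1 to contradict.
2. *Synopsis or section 5.* Section 3.3 contains both statements and links them. It first sets out the model (inflammation raises glutamate, L-IPL function becomes disordered, communication with pain regions changes). It then says what should follow on normalisation if that model is correct. The synopsis gives the model and section 5 gives its testable consequence.
3. *Pilot or test.* Testing a hypothesis within a feasibility study is not a contradiction. The Rationale row of the synopsis and section 3.2 both leave the more definitive evidence to later, larger studies, and 9.1 plans d-z for sizing them.
4. *Three or two.* The synopsis objective, 4.1, 6.3.1 and 9.1 all name connectivity, cohesion and glutamate. The two-item lists group them by modality.

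**Size**

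Inputs from the protocol: alpha 0.05 two-sided (9.1); n = 20 (synopsis); k = 3 constructs, k = 2 if the listed items are counted, k = 4 if ReHo and ALFF (6.2.1) are counted separately. Assumed, because the protocol gives neither: the correlation between outcomes, and 80% power per test.

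Chance of at least one p < 0.05 with no effect, independent tests, 1 − 0.95^k:

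- k = 2: 1 − 0.9025 = 9.75%
- k = 3: 1 − 0.857375 = 14.3%
- k = 4: 1 − 0.814506 = 18.5%

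Simulated paired t-tests with n = 20 and k = 3 give 12.7% at correlation 0.5 and about 10% at 0.8.

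These figures count significance in either direction, whereas the hypothesis predicts a fall in glutamate. Counting only falls for glutamate and either direction for the other two: 1 − 0.975 × 0.95² = 1 − 0.8799 = 12.0%. If all three are directional: 1 − 0.975³ = 1 − 0.9269 = 7.3%.

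Mixed result when all three effects are real, with 80% power each and independence: all significant 0.8³ = 51.2%; none 0.2³ = 0.8%; mixed 100 − 51.2 − 0.8 = 48.0%. By simulation this falls to about 35% at correlation 0.5 and 22% at 0.8.

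The arithmetic is right, but it measures error against a claim the protocol does not make. No section sets a success criterion, promises a familywise 5%, or says that one significant primary confirms the hypothesis. A mixed result is also not an error: each outcome is to be reported with its own test and interval.

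**The case for a change.** The strongest contrary case is that hypothesis, study status and endpoints are protocol content, so a SAP cannot cure an inconsistency among them. The active-versus-sham contrast bears on the section 5 prediction directly. It bears on the synopsis statement only indirectly, because inflammation is not manipulated and every participant must have a raised CRP or ESR (section 5.2). The protocol has also already fixed the primaries, the test and alpha, without saying whether one, all or a named primary decides.

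Part of this stands. The synopsis wording is looser than section 5, and matching the two would be a tidy clerical edit. It is also true that 9.1 states no decision rule. But the looser wording changes no test, estimate or interval, and section 3.3 supplies the link. The decision rule is what a protocol commonly leaves to the SAP, and 9.1 says a SAP will be agreed before unblinding. That the protocol is silent on it is not something stated wrongly.

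The possible remedies do not help the case. A sentence on how to read the p-values would record a policy without altering the analysis. Labelling the matrix-based connectivity results exploratory could demote part of a named primary, since section 6.2.1 derives the connectivity indices from those matrices. That is a choice for the investigators, not the repair of an error.

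**Conclusion.** The concern does not hold. The apparent contradictions disappear when sections 3.3, 4, 4.1, 5, 6.3.1 and 9.1 are read together, and the feasibility status is clear from the synopsis and section 3.2. The remaining gap, how several primaries combine into one conclusion, belongs to the SAP, which was not available here.

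The sizes are conditional. The 9.75% to 18.5% range assumes independent tests and that any one primary could carry a claim; positive correlation or a directional reading lowers it. The 22% to 48% chance of a mixed result rests on an assumed 80% power for each of three real effects. The conclusion would change only if a report presented a single significant primary as confirmation of the section 5 hypothesis, and nothing in the protocol provides for that.
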